8.3.11 Lack of efficacy

When there is deterioration in the cancer, for which the study treatment(s) is being used, may be uncertainty as to whether this is lack of efficacy or an AE. In such cases, unless the the reporting physician considers that the study treatment contributed to the deterioration of the condition, or local regulations state to the contrary, the deterioration should be considered to be a lack of efficacy and not an AE.

8.3.12 Deaths

All deaths that occur during the study, or within the protocol-defined 30-day post-study follow-up period after the administration of the last dose of study treatment, must be reported as follows:

- Death clearly the result of disease progression should be reported to principal investigator and should be documented in the eCRF but should not be reported as an SAE.
- Where death is not due (or not clearly due) to progression of the disease under study, the AE causing the death must be reported to the principal investigator and Astra Zeneca as a SAE within **24 hours** (see Section 8.4.1 for further details). The report should contain a comment regarding the co-involvement of progression of disease, if appropriate, and should assign main and contributory causes of death. This information can be captured in the eCRF.

Deaths with an unknown cause should always be reported as a SAE. A post mortem maybe helpful in the assessment of the cause of death, and if performed a copy of the post-mortem results should be forwarded to AstraZeneca within the usual timeframes.

8.3.13 Olaparib adverse events of special interest

Adverse events of special interest [AESI] are events of scientific and medical interest specific to the further understanding of olaparib's safety profile and require close monitoring and rapid communication by the investigators to AstraZeneca. Adverse Events of Special Interest for olaparib are the Important Potential Risks of MDS/AML, new primary malignancy (other than MDS/AML) and pneumonitis.

A questionnaire will be sent to the principal investigator if an AESI is reported, as an aid to provide further detailed information on the event. During the study there may be other events identified as AESIs that require the use of a questionnaire to help characterise the event and gain a better understanding regarding the relationship between the event and study treatment.

8.4 Safety reporting and medical management

8.4.1 Reporting of serious adverse events

All SAEs have to be reported, whether or not considered causally related to the investigational product, or to the study procedure(s). All SAEs will be recorded in the CRF.

If any SAE occurs in the course of the study, then investigators or other site personnel inform the appropriate AstraZeneca representatives within one day i.e., immediately but **no later than 24 hours** of when he or she becomes aware of it.

The designated AstraZeneca representative works with the investigator to ensure that all the necessary information is provided to the AstraZeneca Patient Safety data entry site **within 1 calendar day** of initial receipt for fatal and life threatening events **and within 5 calendar days** of initial receipt for all other SAEs.

For fatal or life-threatening adverse events where important or relevant information is missing, active follow-up is undertaken immediately. Investigators or other site personnel inform AstraZeneca representatives of any follow-up information on a previously reported SAE within one calendar day i.e., immediately but **no later than 24 hours** of when he or she becomes aware of it.

For further guidance on the definition of a SAE, see Appendix B.

8.4.2 Pregnancy

All pregnancies and outcomes of pregnancy should be reported to AstraZeneca except for:

- If the pregnancy is discovered before the study patient has received any study drug
Pregnancies in the partner of male patients (see Section 5.3 for lifestyle restrictions for male patients with a female partner of childbearing potential and Section 8.4.2.2. for restrictions on male patients fathering a child)

If a pregnancy is reported, the investigator should inform AstraZeneca within 24 hours of learning of the pregnancy.

Abnormal pregnancy outcomes (eg, spontaneous abortion, foetal death, stillbirth, congenital anomalies, ectopic pregnancy) are considered SAEs.

8.4.2.1 Maternal exposure

If a patient becomes pregnant during the course of the study, the investigational products should be discontinued immediately.

Pregnancy itself is not regarded as an adverse event unless there is a suspicion that the investigational product under study may have interfered with the effectiveness of a contraceptive medication. Congenital abnormalities/birth defects and spontaneous miscarriages should be reported and handled as SAEs. Elective abortions without complications should not be handled as AEs. The outcome of all pregnancies (spontaneous miscarriage, elective termination, ectopic pregnancy, normal birth or congenital abnormality) occurring from the date of the first dose of study medication until 6 months after the last dose of study medication should be followed up and documented even if the patient was discontinued from the study.

If any pregnancy occurs in the course of the study, then the Investigator or other site personnel informs overall principal investigator who will discuss with the designated AstraZeneca

representative within 1 day i.e., immediately but **no later than 24 hours** of when he or she becomes aware of it.

The designated AstraZeneca representative works with the Investigator to ensure that all relevant information is provided to the AstraZeneca Patient Safety within 1 or 5 calendar days for SAEs (see Section 9.2.5) and within 30 days for all other pregnancies.

The same timelines apply when outcome information is available.

8.4.2.2 Paternal exposure

Male patients should refrain from fathering a child or donating sperm during the study and for 3 months following the last dose of the investigational products.

Pregnancy of the patient's partners is not considered to be an adverse event. However, the outcome of all pregnancies (spontaneous miscarriage, elective termination, ectopic pregnancy, normal birth or congenital abnormality) occurring from the date of the first dose until 3 months after the last dose should, if possible, be followed up and documented.

8.4.3 Overdose

There is currently no specific treatment in the event of overdose with olaparib or TMZ and possible symptoms of overdose are not established.

Olaparib and TMZ must only be used in accordance with the dosing recommendations in this protocol. Any dose or frequency of dosing that exceeds the dosing regimen specified in this protocol should be reported as an overdose. The Maximum Tolerated Dose is Olaparib 150 mg mg twice daily (tablet) (Days 1-21) with TMZ 75 mg/m² (Days 1-7).

Adverse reactions associated with overdose should be treated symptomatically and should be managed appropriately.

- An overdose with associated AEs is recorded as the AE diagnosis/symptoms on the relevant AE modules in the CRF.

If an overdose on an AstraZeneca study drug occurs in the course of the study, then the Investigator or other site personnel inform appropriate AstraZeneca representatives immediately, or **no later than 24 hours** of when he or she becomes aware of it.

The designated AstraZeneca representative works with the Investigator to ensure that all relevant information is provided to AstraZeneca Patient Safety.

For overdoses associated with a SAE, the standard reporting timelines apply, see Section 8.3.2. For other overdoses, reporting must occur within 30 days.

8.4.4 Medication error

If a medication error occurs in the course of the study, then the Investigator or other site personnel informs the appropriate AstraZeneca representatives within 1 day i.e., immediately but no later than 24 hours of when he or she becomes aware of it.

The designated AstraZeneca representative works with the Investigator to ensure that all relevant information is completed within 1 (Initial Fatal/Life-Threatening or follow up Fatal/Life-Threatening) or 5 (other serious initial and follow up) calendar days if there is an SAE associated with the medication error (see Section 8.3.2) and within 30 days for all other medication errors.

The definition of a Medication Error can be found in Appendix B.

8.4.5 Management of adverse events related to Olaparib and TMZ

Any toxicity observed during the course of the study could be managed by interruption of the dose of the attributed study treatment or dose reductions. Repeat dose interruptions are allowed as required, for a maximum of 4 weeks on each occasion. If the interruption is any longer, the study team must be informed. Olaparib treatment can be dose reduced to 100 mg twice daily. If the reduced dose of 100 mg twice daily is not tolerable, olaparib can be further dose reduced to 100 mg daily, and if this is not tolerable no further dose reduction is allowed and study treatment should be discontinued. Temozolomide can be dose reduced to 60 mg/m² (Days 1-7), and if this is not tolerable TMZ can be further dose reduced to 50 mg/m² (Days 1-7). The following tables should be applied if an AE is deemed to be at least “possibly related” to olaparib, TMZ, or both. If an AE is only attributed to one of the agents the other agent may be continue at an unadjusted dose.

Once dose is reduced, escalation is not permitted (except following concomitant treatment with CYP3A4 inhibitors – see Section 6.5

8.4.5.1 Management of haematological toxicity

Management of anaemia

Table 11 Management of anaemia

Haemoglobin	Action to be taken
Hb < 10 but \geq 8 g/dl (CTCAE Grade 2)*	
First occurrence: Give appropriate supportive treatment and investigate causality. Investigator judgement to continue olaparib and TMZ with supportive treatment (eg transfusion) or interrupt dose for a maximum of 4 weeks. TMZ and olaparib can be restarted if Hb has recovered to > 9 g/dl.
 
Subsequent occurrences: If Hb < 10 but \geq 9 g/dl investigator judgement to continue olaparib and TMZ with supportive treatment (eg transfusion) or dose interrupt (for max of 4 weeks) and upon recovery dose reduction may be considered for olaparib (to 100 mg twice daily as a first step and to 100 mg once daily) and for TMZ (60 mg/m² as a first step and to 50 mg/m² as a second step). If Hb < 9 but \geq 8 g/dl, dose interrupt (for max of 4 weeks) until Hb \geq 9 g/dl and upon recovery dose reduction for olaparib may be considered (to 100 mg twice daily as a first step and to 100 mg once daily as a second step). For TMZ a dose reduction may be considered (to TMZ 60 mg/ m² as a first step and to 50 mg/ m² as a second step).

Hb < 8 g/dl (CTCAE Grade 3)*	
Give appropriate supportive treatment (e.g. transfusion) and investigate causality.
 
Interrupt olaparib and TMZ for a maximum of 4 weeks until improved to Hb \geq 9 g/dl.
 
Upon recovery, for olaparib dose reduce to 100 mg twice daily as a first step and to 100 mg once daily as a second step in the case of repeat Hb decrease. For TMZ dose reduce to TMZ 60 mg/m² as a first step and to 50 mg/m² as a second step.

* If the starting dose of TMZ is lowered as described in section 4.2 the TMZ doses should be adjusted per table 7 based on the starting dose.

Common treatable causes of anaemia (e.g., iron, vitamin B12 or folate deficiencies and hypothyroidism) should be investigated and appropriately managed. In some cases management of anaemia may require blood transfusions. For cases where patients develop prolonged haematological toxicity (≥ 2 week interruption/delay in study treatment due to CTC grade 3 or worse anaemia and/or development of blood transfusion dependence), refer to guidance later in this section for further management.

Management of neutropenia, leukopenia and thrombocytopenia

Table 12 Management of neutropenia, leukopenia and thrombocytopenia

Toxicity	Study treatment dose adjustment
CTCAE Grade 1-2	Investigator judgement to continue treatment or if dose interruption, this should be for a maximum of 4 weeks; appropriate supportive treatment and causality investigation
CTCAE Grade 3-4*	Dose interruption until recovered to CTCAE gr 1 or better for a maximum of 4 weeks. If repeat CTCAE grade 3-4 occurrence, dose reduce olaparib to 100 mg twice daily as a first step and 100 mg once daily as a second step and dose reduce TMZ to 60 mg/m² as a first step and 50 mg/m² as a second step.

* If the starting dose of TMZ is lowered as described in section 4.2 the TMZ dose should be lowered per table 7 based on the starting dose.

Adverse event of neutropenia and leukopenia should be managed as deemed appropriate by the investigator with close follow up and interruption of study drug if CTCAE grade 3 or worse neutropenia occurs.

Primary prophylaxis with Granulocyte colony-stimulating factor (G-CSF) is not recommended, however, if a patient develops febrile neutropenia, study treatment should be stopped and appropriate management including G-CSF should be given according to local hospital guidelines. Please note that G-CSF should not be used within at least 24 h (7 days for pegylated G-CSF) of the last dose of TMZ or olaparib unless absolutely necessary.

Platelet transfusions, if indicated, should be done according to local hospital guidelines.

For cases where patients develop prolonged haematological toxicity (≥ 2 week interruption/delay in study treatment due to CTCAE grade 3 or worse), refer to guidance later in this section for the management of this.

Management of prolonged haematological toxicities while on study treatment

If a patient develops prolonged haematological toxicity such as:

- ≥ 2 week interruption/delay in study treatment due to CTCAE grade 3 or worse anaemia and/or development of blood transfusion dependence
- ≥ 2 week interruption/delay in study treatment due to CTCAE grade 3 or worse neutropenia ($ANC < 1 \times 10^9/L$)
- ≥ 2 week interruption/delay in study treatment due to CTCAE grade 3 or worse thrombocytopenia and/or development of platelet transfusion dependence (Platelets $< 50 \times 10^9/L$)

Check weekly differential blood counts including reticulocytes and peripheral blood smear. If any blood parameters remain clinically abnormal after 4 weeks of dose interruption, the patient should be referred to haematologist for further investigations. Bone marrow analysis and/or blood cytogenetic analysis should be considered at this stage according to standard haematological practice. Study treatment should be discontinued if blood counts do not recover to CTCAE gr 1 or better within 4 weeks of dose interruption.

Development of a confirmed myelodysplastic syndrome or other clonal blood disorder should be reported as an SAE and full reports must be provided by the investigator to AstraZeneca Patient Safety. Study treatment should be discontinued if patient's diagnosis of MDS and/or AML is confirmed.

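### For prolonged anaemia, Table 11 restarts treatment at Hb 9 g/dL while the prolonged-toxicity text stops it short of grade 1 at 4 weeks, and neither is given precedence

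*Combined protocol and SAP*

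**What the plan says.** All the relevant text is in Section 8.4.5.1 of the combined protocol and SAP.

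- **Table 11, grade label.** One row is headed "Hb < 10 but \geq 8 g/dl (CTCAE Grade 2". On the protocol's own scale, then, grade 1 or better begins at 10 g/dL.
- **Table 11, grade 3 row (Hb below 8 g/dL).** The instruction is "Interrupt olaparib and TMZ for a maximum of 4 weeks until improved to Hb \geq 9 g/dl". What follows is continuation at a lower dose: "Upon recovery, for olaparib dose reduce to 100 mg twice daily as a first step", with a parallel step for TMZ.
- **Table 11, grade 2 row.** After a first occurrence, "TMZ and olaparib can be restarted if Hb has recovered to > 9 g/dl". For a later occurrence in which Hb falls below 9, the hold lasts until Hb is at least 9 g/dL.
- **Prolonged toxicity, trigger.** For anaemia, the definition is a hold of at least the length stated here: "2 week interruption/delay in study treatment due to CTCAE grade 3 or worse anaemia and/or development of blood transfusion dependence".
- **Prolonged toxicity, consequence.** "Study treatment should be discontinued if blood counts do not recover to CTCAE gr 1 or better within 4 weeks of dose interruption".
- **Link between the two.** The paragraph under Table 11 sends prolonged cases to the later guidance for further management. It does not say that the later criterion replaces the 9 g/dL threshold.

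**The concern.** Both rules work within the same 4-week limit, but they set different recovery thresholds and lead to opposite outcomes: continued treatment at a lower dose, or permanent discontinuation. Two investigators with the same patient could act differently, and each could cite the protocol.

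The situation is foreseeable. Section 2.3.1 reports that olaparib combined with chemotherapy causes more marrow toxicity, anaemia included, than the agents alone would suggest, and that treatment delays are common. Section 5.1 admits patients with Hb as low as 10.0 g/dL. For a patient who enters at that value, the grade 1 criterion means full return to baseline, whereas Table 11 restarts 1 g/dL below it. Patient safety, drug exposure and consistent recording of discontinuations are at stake.

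**Working it through.** The plan gives no figure to reproduce. The check sets the two rules side by side for a patient who meets the prolonged-toxicity definition.

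**Inputs**
- Grade 2 band: Hb 8 to below 10 g/dL (Table 11 label). Grade 1 or better is therefore Hb 10 g/dL or more.
- Table 11 restart threshold after grade 3 anaemia: Hb 9 g/dL or more, with a hold of at most 4 weeks.
- Prolonged-toxicity criterion: grade 1 or better within 4 weeks, otherwise treatment should be discontinued.

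**Step 1: width of the overlap.** 10 − 9 = 1 g/dL. Values from 9.0 to below 10.0 g/dL meet Table 11's restart condition but are still grade 2.

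**Step 2: outcome for a patient held for grade 3 anaemia and still held at about week 4**

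| Hb at week 4 | Table 11 | Prolonged-toxicity text | Agreement |
|---|---|---|---|
| 10 g/dL or more | Resume at reduced dose | Discontinuation not triggered | Yes |
| 9.0 to below 10.0 g/dL | Resume at reduced dose | Should be discontinued | **No** |
| Below 9 g/dL | Restart condition not met | Should be discontinued | No conflict |

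Example: Hb falls to 7.5, both drugs are held, and Hb is 9.5 at week 4. Table 11 resumes treatment at a reduced dose; the later text discontinues it.

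**Step 3: recovery to 9 g/dL between weeks 2 and 4.** The patient already meets the prolonged definition, yet Table 11 ends the hold before week 4. Suppose treatment restarts at week 3 with Hb 9.5 and Hb remains there. Read literally, grade 1 has not been reached within 4 weeks. Read in sequence, the hold has ended and the test no longer applies. The protocol does not choose between these readings, so this case is ambiguous rather than a direct contradiction.

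**Step 4: who is outside the conflict.** Two groups fall under Table 11 alone: patients with grade 3 anaemia who reach 9 g/dL in under 2 weeks, and patients with grade 2 anaemia who are not transfusion dependent.

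**Step 5: is it specific to anaemia?** Yes. Table 12 holds treatment for grade 3–4 neutropenia, leukopenia or thrombocytopenia until grade 1 or better, for at most 4 weeks. That matches the prolonged-toxicity criterion. Only Table 11 departs from it.

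**Step 6: a smaller point.** Table 11 uses both above 9 and at least 9 g/dL as its restart threshold, so its rows differ at exactly 9.0.

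**The case against.** The best defence is the cross-reference. A general table followed by a referral of prolonged cases to later, more specific text can reasonably be read as letting that text govern. This is a fair reading, but the protocol does not state it. Nor is it clear which rule is the more specific: Table 11 is specific to anaemia, the later text to prolonged toxicity. A second defence is that Table 11 ends the hold at 9 g/dL, so the 4-week test is often never reached. That has force for recovery between weeks 2 and 4, but not for a patient still held at week 4. The later text also says *should*, not *must*. This softens the instruction without removing the opposition.

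A reader might infer more than the documents support, in four ways:

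- **That every patient recovering to Hb 9.0–9.9 g/dL is caught.** The discontinuation rule applies only to prolonged toxicity.
- **That Section 8.4.5 adds a third, conflicting outcome.** On holds beyond 4 weeks it says "If the interruption is any longer, the study team must be informed". That is a duty to notify and is compatible with discontinuation.
- **That the number of affected patients can be stated.** The documents give no rate for the joint event of prolonged toxicity from anaemia and recovery only into the 1 g/dL band.
- **That the primary result is compromised because 4 responses in 30 decide the trial.** Under Section 8.1.2 and note k of the Schedule of Activities, tumour assessments continue after treatment stops for toxicity. Stopping the drugs therefore does not by itself prevent a response from being confirmed. An effect through lost exposure is possible, but nothing in the documents quantifies it.

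**Conclusion.** The inconsistency stands within a defined scope. It concerns patients with prolonged haematological toxicity from anaemia and Hb from 9.0 to below 10.0 g/dL. For those still held at about week 4, the protocol directs both restart and discontinuation. For those who reach 9 g/dL between weeks 2 and 4, it leaves open whether the grade 1 test still applies.

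The conclusion rests on the protocol's own grade labels and on the absence of any statement of precedence; no outside source is needed. The sample size, error rates and decision rule are untouched. The point should be corrected because it bears on safety and exposure and is cheap to resolve. This review takes no position on which threshold is clinically right.

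**What to change.** Reconcile Table 11 with the prolonged-toxicity text in Section 8.4.5.1:

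1. State one recovery criterion for anaemia, in g/dL with the matching CTCAE grade, in both places.
2. State one consequence if it is not met at 4 weeks, in the same words in both places.
3. Say whether the 4-week test still applies to a patient who has already restarted.
4. Use a single inequality at 9 g/dL in Table 11, if that threshold is kept.

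The sponsor's clinical team must choose the criterion and the consequence. The cost is a protocol wording amendment, with no change to the sample size or the analysis.

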8.4.5.2 Management of non-haematological toxicity

Repeat dose interruptions are allowed as required, for a maximum of 4 weeks on each occasion. If the interruption is any longer than this the overall principal investigator must be informed and confirm with the treating physician whether study treatments should continue. Where toxicity reoccurs following re-challenge with study treatment, and where further dose interruptions are considered inadequate for management of toxicity, then the patient should be considered for dose reduction or must permanently discontinue study treatment.

Olaparib can be dose reduced to 100 mg twice daily as a first step and to 100 mg once daily as a second step, while TMZ can be dose reduced to 60 mg/m² as a first step and 50 mg/m² as a second step. Treatment must be interrupted if any NCI-CTCAE grade 3 or 4 adverse event occurs which the investigator considers to be related to administration of study treatment and dose reductions considered or as outlined for specific adverse event management guidelines in section 8.4.5. If the investigator considers the adverse event to be related to only one of the study medications the other medication can continue uninterrupted after discussion with the overall principal investigator if felt to be safe in the opinion of the treating investigator.

Management of new or worsening pulmonary symptom

If new or worsening pulmonary symptoms (e.g., dyspnoea) or radiological abnormalities occur in the absence of a clear diagnosis, an interruption in study treatment dosing is recommended and further diagnostic workup (including a high resolution CT scan) should be performed to exclude pneumonitis.

Following investigation, if no evidence of abnormality is observed on CT imaging and symptoms resolve, then study treatment can be restarted, if deemed appropriate by the investigator. If significant pulmonary abnormalities are identified, these need to be discussed with the principal investigator.

Management of nausea and vomiting

Events of nausea and vomiting are known to be associated with olaparib treatment. These events are generally mild to moderate (CTCAE grade 1 or 2) severity, intermittent and manageable on continued treatment. The first onset generally occurs in the first month of treatment for nausea

and within the first 6 months of treatment for vomiting. For nausea, the incidence generally plateaus at around 9 months, and for vomiting at around 6 to 7 months.

No routine prophylactic anti-emetic treatment is required at the start of study treatment, however, patients should receive appropriate anti-emetic treatment at the first onset of nausea or vomiting and as required thereafter, in accordance with local treatment practice guidelines. Alternatively, olaparib and TMZ tablets can be taken with a light meal/snack (ie 2 pieces of toast or a couple of biscuits).

As per international guidance on anti-emetic use in cancer patients (ESMO, NCCN), generally a single agent antiemetic should be considered eg dopamine receptor antagonist, antihistamines or dexamethasone.

Interruptions for intercurrent non-toxicity related events

Study treatment dose interruption for conditions other than toxicity resolution should be kept as short as possible. If a patient cannot restart study treatment within 4 weeks for resolution of intercurrent conditions not related to disease progression or toxicity, the case should be discussed with overall principal investigator.

All dose reductions and interruptions (including any missed doses), and the reasons for the reductions/interruptions are to be recorded in the eCRF.

Study treatment should be stopped at least 3 days prior to planned surgery. After surgery study treatment can be restarted when the wound has healed. No stoppage of study treatment is required for any needle biopsy procedure.

Study treatment should be discontinued for a minimum of 3 days before a patient undergoes radiation treatment. Study treatment should be restarted within 4 weeks as long as any bone marrow toxicity has recovered.

Because the AEs related to olaparib may include asthenia, fatigue and dizziness, patients should be advised to use caution while driving or using machinery if these symptoms occur.

Table 13 Dose reductions for olaparib

Initial Dose	Following re-challenge post interruption: Dose reduction 1	Dose reduction 2
150 mg twice daily	100 mg twice daily	100 mg once daily

Table 14 Dose reductions for TMZ

Initial Dose	Following re-challenge post interruption: Dose reduction 1	Dose reduction 2
75 mg/m ² (days 1-7)	60 mg/m ² (days 1-7)	50 mg/m ² (days 1-7)
*60 mg/m ² (days 1-7)	50 mg/m ² (days 1-7)	40 mg/m ² (days 1-7)
*50 mg/m ² (days 1-7)	40 mg/m ² (days 1-7)	30 mg/m ² (days 1-7)

* If the starting dose of TMZ is lowered as described in section 4.2.

